### 6.4 Handling of Missing Data

- Missing dates will be handled as follows: For subsequent anti-cancer therapy start date:
  - If only day is missing then: if end date of subsequent anti-cancer therapy is complete, impute to the minimum of (the last day of the month, end date of subsequent anti-cancer therapy); otherwise impute to the last day of the month.
  - If month or year is missing then leave missing.

- For time from initial diagnosis to randomization and time from diagnosis of metastatic disease to randomization, partial dates for initial diagnosis and diagnosis of metastatic disease will be imputed as follows:
  - No imputation will be done if the year is missing
  - If the year is before randomization date then missing days will be imputed as the first day of the month and missing months will be imputed as July
  - If the year is the current year of randomization date then missing days will be imputed as the first day of the month and missing months will be imputed as January
- For duration of AEs, partial dates for **start** of AE will be imputed as follows:
  - Missing day, month, and year should be queried. In case of non-resolution of missing year, then the missing day will be imputed as Cycle 1 Day 1 (C1D1).
  - Start day of AE is missing and the year is same as Cycle 1 Day 1 (C1D1)
    - If the reported month of occurrence of AE is after the month of C1D1 dose then missing day will be imputed as the first day of the month of occurrence of AE.
    - If the reported month of occurrence of AE is the month of C1D1 dose then the missing day will be imputed as the same day as C1D1.
    - If the reported month of AE start date is before the month of C1D1 then the missing day will be imputed as day 15 of the month of AE start date.
    - If the month of AE start date is missing, missing day will be imputed as the date of C1D1.
  - Start day of AE is missing and the year is after the year of C1D1
    - Missing day will be imputed as the first day of the month of occurrence of AE
    - If the month of AE start date is missing, missing day will be imputed as 01 January of the year of AE start date.
- For duration of AEs, partially missing dates for **stop** of AE will be imputed as follows:
  - If the stop date is completely missing, it should be queried. In case of non-resolution of missing year, no imputation will be performed.
  - If only the day is missing, the earlier of the following will be used as the stop date:
    - the last day of the month for stop of AE
    - the later of (last known alive date, AE start date if imputed)

- If month and day are missing, the earlier of the following will be used as the stop date:
  - December 31st of the year for stop of AE
  - the later of (last known alive date, AE start date if imputed)
- For determination of prior medication, any medication with a start date prior to C1D1 will be classified as prior medication regardless of the stop date. Missing or partial dates will be handled as follows:
  - If missing day and/or month of the start date, the medication will be classified as prior unless the month and/or year of the start date is after C1D1
- For determination of concomitant medication, the following will be classified as concomitant medication:
  - Any medication with a start date prior to or on C1D1 and continued after C1D1 (this will be considered as both prior and concomitant medication)
  - Any medication with a start date after C1D1, but prior to the last dose date + 100 days or (date of initiation of subsequent anti-cancer therapy – 1 day), whichever is earlier
- Missing or partial dates for concomitant medication will be handled as follows:
  - If missing day and/or month of the start date, the medication will not be considered as concomitant if the month and/or year of the start date is after the last dose date + 100 days or (date of initiation of subsequent anti-cancer therapy – 1 day), whichever is earlier
  - If missing day and/or month of the stop date, the medication will not be considered as concomitant if the month and/or year of the stop date is prior to C1D1
  - A medication with completely missing start and stop dates will be classified as concomitant
- In order to calculate duration of immune modulating medication for management of drug-related select AEs or IMAEs (as defined in Section 7.2), missing or partial dates for these medications will be handled as follows:

Missing or partial start date:

- If the start date is completely missing, it will not be imputed. Only the number of days that the medication was taken on or after the AE start date will be counted toward the duration of IMM for management of certain AE.
- If only year is provided, impute the start date to January 1st of the year,
- If only day is missing, impute the start date to the first day of the month.

Missing or partial stop date:

- If the stop date is completely missing, impute stop date to the later of (last known alive date, AE start date if imputed)
- If only the day is missing, the earlier of the following will be used as the stop date:
  - the last day of the month for stop of AE
  - the later of (last known alive date, AE start date if imputed)
- If month and day are missing, the earlier of the following will be used as the stop date:
  - December 31st of the year for stop of AE
  - the later of (last known alive date, AE start date if imputed)
- For death date, the following conventions will be used:
  - If the death date is completely missing but reason for death is present, it will be imputed as the last known alive date
  - If the the death date is partially missing (missing day only, or missing both day and month), the death date and corresponding last known alive date will be imputed in 2 steps:
    1. Imputed as 1st of month (missing day only) or January 1st of the year (missing both day and month)
    2. The imputed death date from the 1st step will be compared to the latest alive date captured from multiple sources (unimputed last known alive date), and the maximum of the two will be considered as the imputed death date and last known alive date

No imputation of other missing data is planned.

## 6.5 Stratification and Pooling

For stratified analyses, the randomization stratification factors entered into the IRT system at the time of randomization will be used, as follows:

- PD-L1 status by Dako PD-L1 PharmDx 28-8 assay:  $\geq 1\%$  vs  $< 1\%$  vs indeterminate/not evaluable.

Note: PD-L1 indeterminate/not evaluable will be capped at a maximum of 25% of the total

- Stages of Disease per AJCC 8th edition are stratified as follows: Stage IIIA (LN metastasis  $> 1$  mm)/IIIB vs IIIC vs IIID/IV.

## 6.6 Definitions

- **Baseline:** In general, baseline will be defined as the last assessment result on or before the randomization date (and time if available).

Pre-treatment AEs will be defined as AEs with an onset date prior to but not including the day of the first dose of study treatment.

- **Study Day:** There is no study day zero. In general, Study Day 1 is the date of randomization.
  - For post-randomization days, study day is calculated as: assessment date – randomization date + 1
  - For pre-randomization days, study day is calculated as: assessment date – randomization date

For safety analysis, study day is calculated and presented based on first dose date as defined below.

- **First Dose Date:** First dose date will be defined as the date of first dose, Cycle 1 Day 1 (C1D1). Note, per protocol, first dose date may be  $\leq 5$  days after the date of randomization. If randomization date and first dose date is not on the same day, then date of randomization will be different from C1D1. Safety data will be calculated and presented based on First Dose Date.
- **Treatment-emergent/Extended Treatment-emergent Period:**

For patients on treatment, both the treatment-emergent period and extended treatment-emergent period will be defined as the period of time on or after the day (and time, if collected and not missing) of the first dose of study treatment.

For patients off treatment, the treatment-emergent period is defined as the period of time on or after the day (and time, if collected and not missing) of the first dose of study treatment, until: earlier date of (initiation of new anticancer therapy – 1 day) and (30 days after the date of the last dose of any study treatment).

The extended treatment-emergent period will be defined as the period of time on or after the day (and time, if collected and not missing) of the first dose of study treatment, until earlier date of (initiation of new anticancer therapy – 1 day) and (100 days after the date of the last dose of any study treatment)

- **Treatment-Emergent Adverse Event (TEAE):**

TEAEs are AEs with onset date (and time, if collected and not missing) within the treatment-emergent period, or extended treatment-emergent period depending on the analysis

Incomplete start and end date for TEAEs will be imputed. Any AE will be considered as a TEAE if its status cannot be fully determined because of incomplete data.

- **Last Known Alive Date:** Last known alive date will be defined as the latest alive date on or before data cutoff date, captured from multiple sources. Note that if there is an event date (either an assessment or death) beyond data cutoff date, the last known alive date will be the data cutoff date. If a patient died before or on cutoff date, last known alive date will be set as the death date. Last known alive date will not be imputed, except in the case that the death date is partially missing (see details in section 6.4)

## 6.7 Study Drug Exposure

Analyses will be performed by treatment group “as treated” in Safety Population, unless otherwise specified.

### 6.7.1 Administration of Study Drug

The following parameters will be calculated:

- **Number of cycles:** Total number of complete or partial treatment cycles the patient received
- **Total number of infusions:** Total number of infusions for which the patient received non-zero dose across all cycles
- **Average duration of infusion (min):** Total infusion time (min) / Total number of infusions; where total infusion time = summation of (completion time of infusion – start time of infusion) for all infusions of a patient
- **Relative dose intensity (%)** using the following categories: < 50%; 50 - < 70%; 70 - < 90%; 90 - < 110%; ≥ 110%.
- **Duration of study treatment (days):** Date of last dose – date of first dose (C1D1) + 1

To present duration of study treatment using a Kaplan-Meier curve, the last dosing date will be the event date for those participants who are off study drug. Median duration of study therapy and associated 95% CI will be provided. Participants who are still on study drug will be censored on their last dosing date.

**Table 3 Arm A: Bempegaldesleukin+ Nivolumab Parameter Definitions**

	Bempegaldesleukin	Nivolumab	
		Nivolumab (mg)	Nivolumab (mg/kg) (Patients < 40 kg)
Dosing Schedule per Protocol	0.006 mg/kg Q3W	360 mg Q3W	4.5 mg/kg Q3W
Dose	Dose (mg/kg) is defined as total dose administered at each dosing date (mg) divided by the most recent weight (kg). Dose administered and weight are collected from the CRF	Dose (mg) is defined as the total drug administered at each dosing date as collected on the CRF	Dose (mg/kg) is defined as total dose administered at each dosing date (mg) divided by the most recent weight (kg). Dose administered and weight are collected from the CRF
Cumulative Dose	Cumulative Dose (mg/kg) is the sum of the doses administered to a participant during the treatment period	Cumulative Dose (mg) is sum of all doses administered to a participant during the treatment period	Cumulative Dose (mg/kg) is the sum of the doses administered to a participant during the treatment period
Relative Dose Intensity (%)	Cumulative dose (mg/kg)/[0.006 x (Last dose date - Start dose date + 21)/21] x 100	Cumulative dose (mg) / [(Last dose date - Start dose date + 21) x 360 /21 ] x 100	Cumulative dose (mg/kg) / [ 4.5x (Last dose date - Start dose date + 21) /21 ] x 100
Actual Dose Intensity	Actual dose intensity (mg/kg/week): [Cumulative dose (mg/kg) / (Exposure duration (in days) + 20 days)] x 7	Actual dose intensity (mg/week): [Cumulative dose (mg) / (Exposure duration (in days) + 20 days)] x 7	Actual dose intensity (mg/kg/week): [Cumulative dose (mg/kg) / (Exposure duration (in days) + 20 days)] x 7

**Table 4 Arm B: Nivolumab Parameter Definitions**

	Nivolumab	
	Nivolumab (mg)	Nivolumab (mg/kg) ( Patients < 40 kg)
Dosing Schedule per Protocol	480 mg Q4W	6.0 mg/kg Q4W
Dose	Dose (mg) is defined as the total drug administered at each dosing date as collected on the CRF	Dose (mg/kg) is defined as total dose administered at each dosing date (mg) divided by the most recent weight (kg). Dose administered and weight are collected from the CRF
Cumulative Dose	Cumulative Dose (mg) is sum of all doses administered to a participant during the treatment period	Cumulative Dose (mg/kg) is the sum of the doses administered to a participant during the treatment period
Relative Dose Intensity (%)	$\text{Cumulative dose (mg)} / [ (\text{Last dose date} - \text{Start dose date} + 28) \times 480 / 28 ] \times 100$	$\text{Cumulative dose (mg/kg)} / [ 6 \times (\text{Last dose date} - \text{Start dose date} + 28) / 28 ] \times 100$
Actual Dose Intensity	Actual dose intensity (mg/week): $[\text{Cumulative dose (mg)} / (\text{Exposure duration (in days)} + 27 \text{ days})] \times 7$	Actual dose intensity (mg/kg/week): $[\text{Cumulative dose (mg/kg)} / (\text{Exposure duration (in days)} + 27 \text{ days})] \times 7$

### 6.7.2 Modifications of Study Therapy

Per protocol, for bempedaldesleukin, dose reduction is permitted (as specified in the protocol). This information will be retrieved from CRF dosing pages.

- For participants treated with bempedaldesleukin (NKTR-214), the following will be summarized: Number of participants with dose reduction along with the reason of the dose reduction

Per protocol, for bempedaldesleukin and nivolumab dose delay is permitted (as specified in the protocol).

- Number of participants with dose delay along with the reason of the dose delay

## 6.8 Patient Disposition

A summary of patient disposition will display the number of patients who were randomized by treatment arm. In addition, the number of patients who discontinued study drug and the number of patients who exited the study, both overall and by reason, will be performed by treatment arm for the Safety population. Descriptive statistics for time to study drugs (bempegaldesleukin, nivolumab, bempegaldesleukin or nivolumab) discontinuation (mean, median, min, max) will be summarized for the patients who discontinued study drugs. The follow-up time (time from randomization to the last known alive or death date) will be summarized.

All disposition data will be performed in a data listing.

## 6.9 Study Population

### 6.9.1 Demographics and Other Baseline Disease Characteristics

The following baseline data will be summarized and listed by treatment arms for Safety population:

- Age
- Age categorization (< 65 vs ≥ 65, < 75 vs ≥ 75)
- Gender
- Ethnicity
- Race
- ECOG
- Geographic region (North America, EU vs. Rest of the world)

### 6.9.2 Randomization Stratification Factors

Randomization stratification factors will be summarized for the Safety population by treatment arms.

- PD-L1 Status as Randomized (≥ 1% vs < 1% vs indeterminate/not evaluable) as per EDC.
- Stage as randomized ( IIIA (LN metastases > 1 mm)/IIIB vs IIIC vs IIID/IV) as per EDC.
- Stratification Factor as Randomized as per EDC

$\geq 1\%$  – IIIA (LN metastases  $> 1$  mm)/IIIB vs  $\geq 1\%$  – IIIC vs  $\geq 1\%$  – IIID/IV

$< 1\%$  – IIIA (LN metastases  $> 1$  mm)/IIIB vs  $< 1\%$  – IIIC vs  $< 1\%$  – IIID/IV

Indeterminate/non-evaluable – IIIA (LN metastases  $> 1$  mm)/IIIB vs Indeterminate/non-evaluable – IIIC vs Indeterminate/non-evaluable – IIID/IV

The randomization stratification factors will be listed as per EDC and per IRT. The number of subjects randomized by country will also be summarized.

## 6.10 Treatments and Medications

### 6.10.1 Concomitant Medications

The planned analysis for concomitant medication as described in the protocol will not be performed in this final CSR due to the early termination of this study as a consequence of the closure of the bempegaldesleukin clinical program.

### 6.10.2 Study Drug Exposure

Overall exposure to each study drug will be summarized for the Safety population. Overall exposure to study drugs will be summarized in terms of exposure duration, number of cycles, and relative dose intensity. The following summaries will also be performed:

- Time from randomization to first dose of study therapy (0 to 3 days,  $> 3$  to 7,  $> 7$  to 14,  $> 14$  to 21,  $> 21$ )
- Relative dose intensity (%) using the following categories:  $< 50\%$ ; 50 -  $< 70\%$ ; 70 -  $< 90\%$ ; 90 -  $< 110\%$ ;  $\geq 110\%$
- Overall exposure duration
- Overall cumulative dose
- Number of cycles completed
- Number of infusions
- Average duration of infusion
- Dose-intensity
- The number of patients with at least one dose infusion interruption, the reason for interruption, and the number of infusion interruptions per patient
- The number of patients with at least one dose delay (either study drug) or dose reduction (for bempegaldesleukin only) and their reason(s)

All study exposure data will be performed in a data listing.

## **6.11 Efficacy Analysis**

Due to early termination of the study, all comparative analyses comparing Arm B vs Arm A will not be conducted. Only descriptive analyses by treatment arm will be provided if applicable.

### **6.11.1 Efficacy Analysis of Primary Endpoints**

There is no BICR data transferred for this study due to the early termination of this study as a consequence of the closure of the bempegaldesleukin clinical program. Thus, the planned analysis for the primary efficacy endpoint (RFS by BICR) as described in the protocol will not be performed.

### **6.11.2 Efficacy Analysis of Secondary Endpoints**

#### **6.11.2.1 Overall Survival**

The key secondary endpoint of OS is defined as time from randomization to the date of death from any cause. Patients who do not have a date of death will be censored at their last known alive date. Patients will be followed until their date of death, loss to follow-up, or withdrawal of consent for further follow-up for survival. Patients who do not have any follow-up since randomization will be censored on the date of randomization.

The analysis of OS in the safety population will be conducted by summarizing the number of events, and the descriptive statistics (median and its 95% CI, Q1, Q3, minimum, maximum) based on the Kaplan-Meier estimate will also be summarized by treatment arm. The overall survival rates at 6 and 12 months will be performed by treatment arm.

By-subject listing of OS will be provided.

#### **6.11.2.2 Distant Metastasis-Free Survival**

There is no BICR data transferred for this study due to the early termination of this study as a consequence of the closure of the bempegaldesleukin clinical program. The analysis for DMFS by BICR will not be performed in the CSR.

DMFS by investigator is defined as the time between the date of randomization and the date of first distant metastasis by investigator or date of death due to any cause, whichever occurs first. For patients who remain alive and distant metastasis-free, DMFS will be censored on the date of last disease assessment. DMFS will be evaluated in patients who are Stage III at study entry. The analysis of DMFS by investigator in the Safety population will be conducted by summarizing the

number of events, and the descriptive statistics (median and its 95% CI, Q1, Q3, minimum, maximum) based on the Kaplan-Meier estimate will also be summarized by treatment arm. The DMFS rates at 6 and 12 months will be performed by treatment arm.

### 6.11.2.3 Progression-Free Survival 2

PFS on next-line therapy (PFS2) is defined as the time from randomization to documented progression, per investigator assessment, after the next line of therapy or to death from any cause, whichever occurs first. Patients who were alive and without progression after the next line of therapy will be censored at last known alive date. The following censoring rules will be applied for PFS2:

For a patient who did not receive subsequent anti-cancer therapy:

- If the patient died, the patient is considered as an event on the date of death
- Else, the patient is censored at his/her last known alive date

For a patient who received subsequent anti-cancer therapy:

- If the patient had disease progression after the start of subsequent anti-cancer therapy, the patient is considered as an event on the date of PD
- Else if the patient died or started a second subsequent anti-cancer therapy, the patient is considered as an event at the death date or at the start date of second subsequent therapy whichever is the earliest.
- Else, the patient is censored at his/her last known alive date

The PFS2 by investigator in the safety population will be conducted by summarizing the number of events, and the descriptive statistics (median and its 95% CI, Q1, Q3, minimum, maximum) based on the Kaplan-Meier estimate will also be summarized by treatment arm. The PFS2 rate at 6, and 12 months will be performed by treatment arm.

### 6.11.2.4 PD-L1 Expression as a Predictive Biomarker for RFS per BICR

There is no BICR data transferred for this study due to the early termination of this study, which resulted from the decision to end the global clinical development program for bempegaldesleukin in combination with Nivolumab. Thus, the planned analysis for PD-L1 expression as a predictive biomarker for RFS per BICR as described in the protocol will not be performed.

### 6.11.2.5 Patient-Reported Outcomes (PROs)

The analysis of EORTC QLQ-C30 data will be performed in the Safety population. Scores for all EORTC QLQ-C30 items and subscales will be linearly transformed to a 0 to 100 metric where higher values indicate better functioning/well-being or lower symptom burden (see EORTC QLQ-C30 Scoring Manual). The primary domains of interest for the HRQoL analysis are GH/QoL and physical functioning of EORTC QLQ-C30.

Scores and post-baseline mean score changes and percent of subjects' HRQoL response status (e.g., improved, worsened, no change) compared to their baseline for the EORTC QLQ-C30 primary subscales will be summarized (e.g., mean with standard deviation and 95% CI, median, minimum, maximum) by treatment group and assessment time point. The clinically meaningful change for group-level analysis will be defined for each EORTC QLQ-30 domain as recommended by the literature ([Musoro, 2018](#)), specifically as 7 for GH/QoL and 5 for physical functioning. For individual-level analysis (i.e., percent of subjects who achieved the HRQoL change), the clinically meaningful change thresholds will be defined as 5 (-5) for improvement (deterioration) for both GH/QoL and physical functioning ([Cocks, 2015](#)).

The primary time point of interest will be Day 1 of Cycle 1 and Day 1 of Cycle 2-17 for Arm A, and Day 1 of Cycle 1 and Day 1 of Cycle 2-3 for Arm B.

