Procedure ^a	Arm A Bempegaldesleukin (NKTR-214) and Nivolumab Cycle = 3 Weeks (21 days)						Notes
	Cycle 1				Cycles 2-17		
	Day 1 (≤ 5 days post-randomization)	Day 3 (-1 day)	Day 5 (± 1 day)	Day 8 (± 1 day)	Day 1 (± 3 days)	Day 4 (± 1 day) (call or visit)	
Safety Assessments							
Targeted Physical Exam	X				X		Prior to dosing
Vital Signs and Weight	X				X		
 • Predose (bempegaldesleukin); includes blood pressure, pulse, respiratory rate, temperature, and weight (see Section 8.18) • Within 30 minutes after the end of nivolumab infusion; includes blood pressure, pulse, respiratory rate, and temperature (see Section 8.18)
Local Laboratory Tests	X				X		Within 24 hours (or as soon as locally feasible) prior to dosing to inform dosing decision; see Appendix 1
Local Pregnancy Test	X				X		Serum or urine pregnancy test (minimum sensitivity equivalent units 25 IU/L or equivalent units of HCG) is required within 24 hours prior to dosing in WOCBP to inform dosing decision; see Section 8.13.1
Central Laboratory Tests	X				X		Within 5 days prior to dosing; see Appendix 1
Performance Status	X				X		See Appendix 3
Adverse Events	Continuous assessment						Record at each visit
Concomitant Medications and Procedures	Continuous assessment						Record at each visit

Procedure ^a	Arm A Bempegaldesleukin (NKTR-214) and Nivolumab Cycle = 3 Weeks (21 days)						Notes
	Cycle 1				Cycles 2-17		
	Day 1 (≤ 5 days post-randomization)	Day 3 (-1 day)	Day 5 (± 1 day)	Day 8 (± 1 day)	Day 1 (± 3 days)	Day 4 (± 1 day) (call or visit)	
Pharmacokinetic and Exploratory Biomarker Samples							
PK and Immunogenicity Blood Samples	See Section 5.7 and Table 10 for details						
Biomarker Samples	See Section 5.8 XXXXXXXXXX						
CVA Biomarker Samples	See Section 5.8.2.4 for details						
Outcomes Research Assessments							
EORTC QLQ-C30	X				X		Predose (may be administered by telephone); performed for those ≥ 18 years of age at the time of informed consent, before any other study related procedures, and before the EQ-5D-5L; see Section 5.9 for additional details
EQ-5D-5L	X				X		Predose (may be administered by telephone); performed for those ≥ 18 years of age at the time of informed consent, before any other study-related procedures, and after the EORTC QLQ-C30; see Section 5.9 for additional details

Procedure ^a	Arm A Bempegaldesleukin (NKTR-214) and Nivolumab Cycle = 3 Weeks (21 days)						Notes
	Cycle 1				Cycles 2-17		

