Note: If scheduled visits or assessments coincide with a weekend or holiday, schedule at the next feasible date. Please contact the Medical Monitor to discuss any concerns about study visits or assessments that may fall out of the protocol-specified window because of unforeseen delays or other patient-specific circumstances. All out of window visits and procedures will incur a protocol deviation.

Table 3: On-Treatment Schedule of Events for Arm B

Procedure ^a	Arm B Nivolumab Cycle = 4 Weeks (28 days)			Notes
	Cycle 1		Cycles 2-13	
	Day 1 (≤ 5 days post- randomization)	Day 8 (± 1 day)	Day 1 (± 3 days)	
Study Drug				
Study Drug Administration	X		X	Dispense and administer study drugs following all predose assessments. Following first dose, subsequent doses of study drug may be administered no less than 25 days after prior dose of study drug. If needed, flush the IV line with an appropriate amount of diluent after the nivolumab infusion. Refer to Section 5.3.2 and Pharmacy Manual for details.
Safety Assessments				
Targeted Physical Exam	X		X	Prior to dosing
Vital Signs and Weight	X		X	
 Predose; includes blood pressure, pulse, respiratory rate, temperature, and weight (see Section 8.18) Within 30 minutes after the end of nivolumab infusion; includes blood pressure, pulse, respiratory rate, and temperature (see Section 8.18)
Local Laboratory Tests	X		X	Within 24 hours (or as soon as locally feasible) prior to dosing to inform dosing decision; see Appendix 1
Local Pregnancy Test	X		X	Serum or urine pregnancy test (minimum sensitivity equivalent units 25 IU/L or equivalent units of HCG) is required within 24 hours prior to dosing in WOCBP to inform dosing decision; see Section 8.13.1
Central Laboratory Tests	X		X	Within 5 days prior to dosing; see Appendix 1
Performance Status	X		X	See Appendix 3

Procedure ^a	Arm B Nivolumab Cycle = 4 Weeks (28 days)			Notes
	Cycle 1		Cycles 2-13	
	Day 1 (≤ 5 days post-randomization)	Day 8 (± 1 day)	Day 1 (± 3 days)	
Adverse Events	Continuous assessment			Record at each visit
Concomitant Medications and Procedures	Continuous assessment			Record at each visit
Pharmacokinetic [REDACTED] Biomarker Samples				
PK and Immunogenicity Blood Samples	See Section 5.7 and Table 10 for details			
Biomarker Samples	See Section 5.8 and Table 11 for details			
CVA biomarker samples	See Section 5.8.2.4 for details			
Outcomes Research Assessments				

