## 5.2 Study Medications

Within 5 calendar days following randomization, the patient should receive the first dose of study treatment. Table 1 provides the timing of study drug administration.

Patients will be treated for approximately 1 year (maximum of 17 cycles for Arm A and 13 cycles for Arm B) or until disease recurrence, death, unacceptable toxicity, symptomatic deterioration, decision by investigator to discontinue treatment, decision by patient to discontinue treatment or withdraw consent from the study, patient is lost to follow-up, or decision by Sponsor to terminate the trial, whichever is earlier.

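### The QLQ-C30 time points are named by cycle number with no link to weeks, although cycles last 3 weeks in Arm A and 4 weeks in Arm B, so equal cycle labels are not equal times

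*SAP*

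**What the plan says.** SAP 6.11.2.5 plans scores, mean changes from baseline and the percentages improved, worsened or unchanged for global health/QoL and physical functioning, "by treatment group and assessment time point". It then lists the time points that matter most, separately for each arm. The combination arm has "Day 1 of Cycle 1 and Day 1 of Cycle 2-17 for Arm A". The list for the monotherapy arm is much shorter and stops after the third cycle: "Day 1 of Cycle 1 and Day 1 of Cycle 2-3 for Arm B". Protocol 9.6.2 has the same summary layout but names no cycles.

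The cycles differ in length. The protocol schedule of events (Section 1.2) gives "Cycle = 3 Weeks (21 days)" for Arm A in Table 2 and "Cycle = 4 Weeks (28 days)" for Arm B in Table 3. Both tables place the QLQ-C30 before dosing on Day 1 of every cycle, through Cycle 17 in Arm A and Cycle 13 in Arm B. SAP 5.2 gives the same limits: "maximum of 17 cycles for Arm A and 13 cycles for Arm B".

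SAP 6.11 states that "all comparative analyses comparing Arm B vs Arm A will not be conducted" because the study ended early, and that "Only descriptive analyses by treatment arm will be provided if applicable".

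**The concern.** A cycle number is a dosing count, and here the two arms count at different speeds. A score labelled Cycle 9 in Arm A is taken earlier after randomization than one labelled Cycle 9 in Arm B. Time since surgery, cumulative exposure and the chance of having recurred or stopped treatment all differ between those two moments. Dose delays loosen the link further. Protocol 5.3 lets treatment run past one year to complete the cycles, and Protocol 5.10 delays both Arm A drugs when either one meets its delay criteria.

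The two subscales are secondary endpoints, and the SAP still plans means, 95% confidence intervals and responder percentages for each arm. If results carrying the same cycle label are read across arms, part of any apparent difference is a difference in timing. The SAP neither aligns the time points nor warns against reading them that way.

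**Working it through.** **Inputs.** Cycle lengths of 3 and 4 weeks (Protocol 1.2, Tables 2 and 3). Maximum cycles of 17 and 13 (SAP 5.2; Protocol 5.3). SAP time points: Arm A Cycles 1 to 17, Arm B Cycles 1 to 3 (SAP 6.11.2.5). Protocol questionnaire visits in Arm B: Cycles 1 to 13 (Table 3).

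**The plan's own figure.** The documents give no figure for the timing gap. They do give a treatment duration of about one year: 17 × 3 = 51 weeks in Arm A and 13 × 4 = 52 weeks in Arm B. Both agree, so the inputs are consistent.

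**Nominal week of Cycle k Day 1, counted from Cycle 1 Day 1.**
- Arm A: 3(k-1)
- Arm B: 4(k-1)
- Gap at the same cycle number: 4(k-1) - 3(k-1) = k-1 weeks

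| Cycle | Arm A week | Arm B week | Gap (weeks) | Arm B cycle listed in SAP 6.11.2.5? |
|---|---|---|---|---|
| 2 | 3 | 4 | 1 | yes |
| 3 | 6 | 8 | 2 | yes |
| 5 | 12 | 16 | 4 | no (protocol only) |
| 9 | 24 | 32 | 8 | no (protocol only) |
| 13 | 36 | 48 | 12 | no (protocol only) |

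Arm A Cycles 14 to 17 (weeks 39 to 48) have no Arm B cycle of the same number on either list.

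**Where the schedules meet.** The common multiples of 3 and 4 up to week 48 are 0, 12, 24, 36 and 48.

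| Week | Arm A cycle | Arm B cycle |
|---|---|---|
| 0 | 1 | 1 |
| 12 | 5 | 4 |
| 24 | 9 | 7 |
| 36 | 13 | 10 |
| 48 | 17 | 13 |

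Every other Day 1 visit lies within 2 weeks of a Day 1 visit in the other arm. Protocol Table 10 uses the same later pairs (Arm A Cycles 5, 9, 13, 17; Arm B Cycles 4, 7, 10, 13) for pharmacokinetic and immunogenicity sampling, though it does not say that alignment was the reason.

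**Is a calendar scale available?** Yes. SAP 6.6 defines study day from randomization. SAP 6.11.2 reports OS, DMFS, PFS2 and investigator-assessed RFS at 6 and 12 months. The protocol times imaging from randomization and keeps it there when doses are delayed.

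**The case against.** The strongest reply is that nothing is being compared. SAP 3.0, 4.0 and 6.11 remove every Arm A versus Arm B analysis, and the PRO objective is to describe change from baseline, which is a within-arm question. A reader might infer that the plan compares the arms at mismatched times and so yields a biased effect. The documents do not support that, because no PRO test or arm difference is planned. This part of the objection stands in full.

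Two further limits also stand. A reader might picture one table row holding both arms at the same cycle, but the SAP specifies no layout and lists the cycles separately for each arm. A reader might also take 12 weeks as the gap on the SAP's own text. With Arm B stopping at Cycle 3, as printed, the gap is at most 2 weeks, and 12 weeks requires the protocol's Cycles 2 to 13.

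It can also be said that predose cycle visits are how the data are collected, that the follow-up questionnaires are not tied to cycles, and that SAP 6.1 promises listings of all data. Study day makes the timing of each assessment recoverable. All of this is true, and it lowers the stakes. It does not make cycle number a common time scale, and listings do not repair a summary that readers will look at first. A footnote giving the nominal week would be a lighter remedy, but it would not handle assessments that shift with dose delays.

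**Conclusion.** The point holds as a matter of presentation. The time points of interest are named by cycle, the cycle lengths differ, and no mapping to weeks exists for these data. Equal cycle numbers are k-1 nominal weeks apart: up to 2 weeks on the SAP as printed, and up to 12 weeks on the protocol's Arm B schedule. No test or estimate is affected. What is at risk is the reading of descriptive summaries of two secondary endpoints.

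The sizes assume on-schedule dosing. Allowed visit windows, a first dose up to 5 days after randomization, and dose delays all move the actual dates. Delays could widen or narrow the gap, and the documents give no basis for saying which. The documents also do not say how many patients reached the later cycles, where the nominal gap is largest. The change is worth making because it is cheap and puts these summaries on the kind of calendar scale already used for the survival endpoints.

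**What to change.** In SAP 6.11.2.5:

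1. Reconcile the Arm B list, printed as Cycle 2-3, with Cycles 2-13 in Protocol Table 3.
2. Summarise QLQ-C30 by weeks since randomization. Assign each assessment by its actual date to a stated window, and include windows centred on weeks 12, 24, 36 and 48. State the window width, and the rule for choosing when two assessments fall in one window.
3. Say that these weeks nominally match Arm A Cycles 5, 9, 13, 17 and Arm B Cycles 4, 7, 10, 13, but that assignment follows the date and not the cycle number.
4. Keep the by-cycle summaries as supportive, labelled with nominal week and with a note that cycle rows are not to be read across arms.

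**Cost.** SAP wording and one visit-window derivation from the study day already defined in SAP 6.6; no new visits or data. The downside is that fewer assessments sit at the highlighted time points. On schedule, these are 4 of 16 post-baseline on-treatment visits in Arm A and 4 of 12 in Arm B. The retained by-cycle summaries still show the rest.
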